## **4.5 Data analysis**

### **4.5.1 WP1 Qualitative interviews**

Interview data will be analysed by the Research Fellow (RF), supported by Qualitative co-applicant lead [name], following Braun and Clarke's six stage process for reflexive thematic analysis (TA). An inductive orientation will ensure the analysis is driven by data, rather than by existing theoretical constructs. Lumivero NVivo qualitative data analysis software will be used for data management and analysis.

The analysis phases will be:

1. Familiarisation with the data
2. Generation of initial codes to identify data items which represent units of meaning relevant to the research questions
3. Generation of candidate themes representing conceptually similar codes
4. Review and reorganisation of themes to reflect the most significant patterns in the data
5. Naming and refinement of themes in relation to core concepts
6. Reporting.

Prior to the writing and dissemination of the final summary report, themes will be presented for review by our Public Contributors to gain their interpretation and inform dissemination of findings. To ensure rigour, oversight will be provided by the research team throughout the analysis process.

#### **4.5.2 WP2 Healthcare professional e-survey**

As this is an exploratory study, sample size calculations are not necessary, but we will aim to recruit a minimum of 50 participants to draw preliminary conclusions. Survey response data in Qualtrics will be downloaded as an SPSS file onto a secure UWE Bristol OneDrive folder. Anonymised data will be securely transferred from UWE to Dorothy House and only members of the research team will have access to this information. Data will be analysed by the RF, supported by Quantitative co-applicant lead [name]. Free text responses will be analysed using content analysis. Quantitative responses will be analysed using descriptive statistics, with categorical variables summarised as frequencies (%) and continuous variables summarised as medians (interquartile ranges).

#### **4.5.3 WP3 Stakeholder Focus Groups**

Transcribed data will be uploaded onto NVivo, and analysed by RF, supported by project lead [name], using inductive qualitative content analysis in a three-phase process.

1. Preparation phase: collecting suitable data, making sense of the data and selecting the unit of analysis. Each focus group transcript will be considered a single 'unit of analysis' as large enough to be considered whole but small enough to be kept in mind during the analysis process. Transcribed text will be categorised into content areas (approximately 6), or NVivo 'parent nodes', that reflect the questions asked in the stakeholder focus groups.
2. Organisation phase: open coding, creating categories and abstraction. Headings will be attributed to the text, and categories freely generated (open coding). Categories will be compared and grouped into higher order categories, where text appears to 'belong together'. During abstraction, categories will be re-compared and re-grouped and put into a hierarchical model of closeness to distance from the text.
3. Reporting phase: The content of the categories will be described and reported in detail to our Public Contributors and the research team to

increase trustworthiness of findings, prior to publication. The findings will be presented as clinical and research recommendations for PSC, to help people with inflammatory arthritis to live well over the course of their disease. We will particularly consider Supportive Care, within the 'six pillars' framework, as this includes improving a person's general physical and mental health..

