## **2 THEORETICAL FRAMEWORK**

This project comprises three discrete and iterative work-packages (WP). Qualitative methods have been selected for work-package 1 (WP1) which explores with people living with an inflammatory arthritis, what their understanding and perspectives are of PSC, and how PSC may support them to live well. Semi-structured interviews are the optimal method to explore a topic where little prior knowledge exists, and in the context of the lived experience. Semi-structured interviews allow for core topics to be raised for discussion but give scope for participants to raise unanticipated issues; the use of a topic guide facilitates the discussion but the precise wording and order of questions is contextual and responsive to the participant's account.

Work-package 2 (WP2) aims to explore (1) Rheumatology, General Practice and Community healthcare professionals' (HCP) views on PSC, and (2) Palliative Care HCPs' views on Inflammatory Arthritis and Supportive Care, how they currently collaborate, and how PSC may help people with Inflammatory arthritis to live well. As this work seeks to capture a large volume of data from a range of different populations at a single time point, then a survey format is appropriate. The majority of the survey data will be quantitative to ensure forced choice responses for clarity of data, and ease of data analysis.

The final work-package (WP3) will take a qualitative approach as it aims to explore the views of stakeholders, where no prior expectations have been set. Focus groups provide an opportunity for exploration of a topic, facilitated by a topic guide, to elicit the range of opinions and recommendations within the group. They can also enable group consensus on a topic where this is required.

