### **3 STUDY AIMS, OBJECTIVES, RESEARCH QUESTIONS & OUTCOMES**

#### **3.1 Aims:**

- To explore the potential role of PSC for people with inflammatory arthritis.
- Describe any unmet patient need.
- Develop clinical and research recommendations to help people with inflammatory arthritis to live well over the course of their disease.

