**4.4.4. Data collection** Data from WP1 and 2 will be assimilated into a 'key findings' presentation to be shared with expert stakeholders. Pre-application rapid literature review will be repeated and any new findings included in this presentation. A summary of the project's findings, and links to the three videos used, will be sent to participants prior to the online event/s to optimise the potential for reflective and deep discussion. This summary will be used as a topic guide to steer the discussion to key questions. Focus groups will be conducted face to face (x2) and online (x2) via Microsoft Teams at a date and time convenient to participants, and following **participant consent**, recorded using embedded audio recording function. Each focus group will run for a maximum of 120 mins. Discussion will broadly focus on:

- What would 'good' look like for people with Inflammatory arthritis to live well with support from PSC services?
- How would this be measured?
- What is the current unmet need?
- What could reduce/address this unmet need in Rheumatology and Palliative care services?
- What are the challenges and barriers?
- What further clinical and/or research work is required?

After each event, the discussion will be summarised by the lead facilitator ([name] or [name]) and confirmed by members of the group. An iterative approach will be taken across these events so the final summary is representative of the discussion from all Stakeholder events. For example, in groups 2 and 3, following initial discussion and agreement of draft recommendations, the views of the previous Stakeholder group/s will be shared and added to or refined. Using transcribe function within Microsoft 365, audio data will be transcribed verbatim and analysed using inductive qualitative content analysis.

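### WP3's main prompts and reporting sentence presuppose unmet need and a role for PSC, and the protocol does not say how a null, contrary or divided view would be reported

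*Protocol*

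**What the plan says.** **Stated stance.** Section 3.1 gives two open aims: "To explore the potential role of PSC for people with inflammatory arthritis" and "Describe any unmet patient need". Section 2 justifies a qualitative WP3 because "it aims to explore the views of stakeholders, where no prior expectations have been set".

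**Prompts.** Section 4.4.4 lists six points on which discussion will broadly focus. In order:

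1. "What would 'good' look like for people with Inflammatory arthritis to live well with support from PSC services"
2. how this would be measured
3. "What is the current unmet need"
4. "What could reduce/address this unmet need in Rheumatology and Palliative care services"
5. "What are the challenges and barriers"
6. what further clinical or research work is required

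**Analysis and reporting.** Under Section 4.5.3 the transcripts are sorted into about six content areas that mirror the questions put to the groups, and are then coded openly. The reporting phase states: "The findings will be presented as clinical and research recommendations for PSC, to help people with inflammatory arthritis to live well".

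**Use of the output.** Section 3.4 makes the description of unmet need and the recommendations primary outcomes. The recommendations will be shared with patients, clinicians, academics and service commissioners, and later work is to look at putting them into practice.

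**The concern.** An exploratory study that asks whether a service has a role should leave room for the answer that it has none, has one only for some people, or is disputed. Here the aims leave that room, but the wording of the WP3 prompts and of the reporting sentence does not. A group asked what good PSC support would look like, and what the unmet need is, starts from the premise that both exist. A report whose form is fixed as recommendations for PSC has no stated place for a group that doubts the premise.

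What is at stake is how the output can be read. If stakeholders recommend PSC, a commissioner would want to know whether they were asked if it was warranted. Under the present wording the report could not show that they were. Favourable recommendations would then be hard to tell apart from the effect of the framing.

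**Working it through.** No sample size, power or error rate is involved, so nothing is recomputed. The check is to classify the six prompts in Section 4.4.4, and then look for any route by which a negative or divided result would be reported.

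**Step 1: classify the prompts.**

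| Prompt | Topic | Premise |
|---|---|---|
| 1 | What good looks like with PSC support | PSC support taken as given |
| 2 | How it would be measured | Depends on prompt 1 |
| 3 | The current unmet need | Unmet need taken as given |
| 4 | What could reduce that need | Unmet need taken as given, but Rheumatology is named alongside Palliative Care |
| 5 | Challenges and barriers | Neutral |
| 6 | Further work | Neutral |

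The count is 1 (PSC support) + 1 (dependent) + 2 (unmet need) + 2 (neutral) = 6. The number that ask whether there is unmet need, or whether PSC is a suitable response, is 0.

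**Step 2: follow the prompts into the analysis.** Section 4.5.3 derives the content areas from the questions asked. A question that was not asked has no content area of its own. Open coding works inside those areas, so a doubt voiced by a participant can be coded, but only under a heading that assumes the thing doubted.

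**Step 3: look for a reporting route.** Sections 4.4.4 and 4.5.3 contain no statement on how a finding of no need, no role at some stage, a need better met elsewhere, or disagreement would be presented. Section 4.4.4 has later groups see earlier groups' views after agreeing draft recommendations, and these are then added to or refined. Rejecting them is not mentioned.

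**Step 4: compare with the rest of the protocol.** The narrowing is not confined to one sentence. Sections 3.2, 3.3, 3.4 and 4.4 all speak of the nature and scope of unmet need rather than its existence. The fourth research question in Section 3.3 asks for recommendations to help people live well by way of PSC. The WP2 survey items described in Section 4.3.4 as following the video ask how, and in what circumstances, PSC may help. Section 6.3 expects most WP3 participants to be volunteers from WP1 and WP2, so the groups will mainly be people already engaged with the topic through this study.

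**Result.** Set beside Sections 2 and 3.1, four of the six prompts (three directly and one by dependence) and the reporting sentence are less open than the stance the protocol claims for WP3.

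**The case against.** The strongest reply is that this is exploratory qualitative work with no formal decision rule, and that the protocol has several openings for contrary views.

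- The prompts are an outline of what discussion will broadly cover, not a script. The barriers prompt does not mention PSC and can draw adverse opinion, and the further-work prompt is neutral.
- Prompt 4 names Rheumatology services, and the purpose of WP3 stated in Section 4.4 covers Primary Care and Community services too. Responses other than PSC are within scope.
- Coding is inductive, category content is to be reported in detail to the Public Contributors and research team, and group members confirm each summary.
- WP3 does not start cold. WP1 asks for views on PSC before and after the video, WP2 sets out to gauge the value of PSC and the circumstances in which it may help, and both feed the summary that serves as the WP3 topic guide. Section 3.2 ties the unmet need to what those data describe.
- Recommendations for PSC can be read as recommendations about PSC. Section 3.4 says they describe its potential role, which could be a narrow one.

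All of this stands, and it limits the point. A reader might infer that the study will endorse PSC whatever stakeholders say. The documents do not support that: the form of the output is fixed, its content is not, and a limited role or a call for more research would fit. A reader might also infer that the problem is worst in early disease. The literature review in Section 1 is not broken down by disease stage, so that cannot be shown.

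The reply leaves two gaps. No prompt puts the questions of need and suitability directly, and no sentence says what happens to a negative or divided answer. Earlier work-packages do not close the second gap, because the recommendations are written from WP3.

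**Conclusion.** The point holds as an inconsistency between the stated stance and the planned procedure. The leading wording could tilt a primary outcome towards PSC, and a null, contrary or divided view has no stated route into the report. It does not show that the conclusion is settled in advance, and the size of any tilt cannot be estimated from the document.

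The judgement assumes that the prompts are used broadly as written and that no separate topic guide already asks the open questions. If facilitators do ask them, the remaining fault is the missing reporting commitment in Section 4.5.3. This is a cheap improvement worth making before WP3 begins, not a flaw that undermines the study.

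**What to change.** **Section 4.4.4.** Open the discussion with two questions, and only then ask what good would look like:

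- *What needs, if any, are not met by current services, and which service is best placed to meet each?* (in place of the present unmet-need prompt)
- *Does PSC have a role for people with inflammatory arthritis: for whom and at which stage, and for whom or when not?*

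**Section 4.5.3.** Replace the reporting sentence with wording such as: *Findings will be presented as recommendations on the role of PSC. No identified need, no role at a given stage, a need better met elsewhere, or disagreement between participants will each be reported as a conclusion.*

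The report should not count how many of the four groups supported each role. Later groups see and refine the views of earlier ones, so the groups are not independent and a tally would mislead.

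**Cost.** A wording change to the protocol and to the summary used as topic guide, handled as an amendment under Section 7.2 before WP3 starts. It takes a few minutes of each 120-minute group, and the recommendations may turn out narrower. No extra participants are needed.

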## **5. STUDY SETTING**

The majority of this study collects data online (WP1, WP2 and 2 focus groups in WP3). The two face to face focus groups in WP3 will be conducted at Dorothy House Hospice.

## **6. STUDY RECRUITMENT AND WITHDRAWAL**

### **6.1 Work-package 1**

We have allocated four months for recruitment and the conduct of interviews. We have deliberately sought agreement from a large number of organisations (Bath and Bristol Rheumatology clinics; Bristol Bone and Joint Health Integration Team; Bath Institute for Rheumatic Diseases; Dorothy House Hospice and wider national hospice network; Sawubona (We See You) and Bath and Bristol Research Engagement Networks). We do not anticipate any problems in recruiting a minimum of 6 people per month, for example, the Bristol and Bath Rheumatology services see approximately 500 people with inflammatory arthritis per month, and Dorothy House Hospice, has had, on average, 10 people with inflammatory arthritis referred every month for the past two years. We will monitor recruitment rate closely and if any concerns arise that we may not hit our recruitment timeline, then we will advertise on social media.

Interview participants will not be paid or incentivised to take part.

### **6.2 Work-package 2**

We have allocated three months for the e-survey to be 'live' to recruitment, and to reach a minimum of 50 participants. We consider this to be realistic based on similar surveys our research team have conducted in the past two years. For example, a recent national, online survey of healthcare professionals recruited 77 participants over a three-month period via professional networks and social media. The project timelines have flexibility within them for us to extend the survey for a further month if required.

### **6.3 Work-package 3**

The majority of participants in our four stakeholder focus groups will be volunteers from WP1 and 2. If at the end of those work-packages we have any concerns about the number of volunteers then we will actively seek additional participants via our established patient and public collaborators, and professional networks.

Focus group participants will be given a £25 voucher as a 'thank you'.

## **6.4 Withdrawal from the study**

WP1: Participants will be advised during data collection that they can pause or stop the interview at any time if they wish to do so. Each participant also has the right to withdraw from the study for up to two weeks after their interview. This means that any recording and transcription related to them will be deleted at that point, and they will not be contacted further. However, it will not be possible to exclude their data if they request to withdraw after two weeks, as their data may already be included in the analysis. Participants will be made aware of this via the participant information sheet.

WP2: Completion and submission of the survey is voluntary. Once a participant submits their survey, it will not be possible to withdraw their data. Participants will be made aware of this via the participant information sheet.

WP3: Participation in the focus groups is voluntary. Participants can withdraw at any time during the event. It will not be possible to remove a participant's individual contribution in the recording of these focus groups. Participants will be informed that these focus groups will be recorded in the participant information sheet and again at the start of workshop. At the end of the focus group all participants will be reminded that the focus group was recorded and data will be anonymised. If a participant has a particular response they would like to withdraw, then a note will be made of this and that part of their contribution will not be included in the final data set.

## **7 ETHICAL AND REGULATORY CONSIDERATIONS**

### **7.1. Assessment and management of risk**

At the onset of the project, a full risk assessment and data protection impact assessment will be conducted, and issues identified, and mitigations found.

Training needs of research staff or our Public Contributors will be identified and training completed, this will be supported by our local RDN as they have a suite of research delivery training for research staff and the public.

The project involves interviews, a survey, and stakeholder focus groups with human participants who are either healthcare professionals, or recipients of healthcare services, including from the NHS and hospices. NHS Ethical and HRA approvals will be sought prior to the commencement of participant recruitment.

We will have a process for adverse events. A distress protocol will be compiled and adhered to in the event of any emotional issues arising amongst participants and a list of sources of support will be available.

A Steering group will monitor progress of the project and ensure all issues are considered in a timely way, and we will benefit from a range of expertise from members. Membership will include: at least one Public Contributor; experts in the project's methods; clinical academic expertise in Rheumatology and Palliative Care, and ICB representation.

BSW Research Hub will also help with all aspects of research governance and sponsor support, as our local R&D office. This includes helping with and ensuring all relevant regulatory and ethical approvals are in place before the study commences.

## **7.2 Research Ethics Committee (REC), other Regulatory review & compliance and amendments**

The Chief Investigator will ensure this study is conducted in accordance with the principles of the Declaration of Helsinki and with relevant regulations and with Good Clinical Practice.

The protocol, participant information sheet, and consent form will be submitted for HRA and NHS Ethical Approval by a member of the study team. Further approvals will be sought from the UWE ethics committee, BSW Research Hub and via the internal DHHC research governance process. Formal approval will be obtained from recruitment centres via Participant Identification Centre documentation. Participant recruitment will not commence until these approvals have been gained.

The Chief Investigator will review any requests to amend the protocol and will decide whether an amendment is substantial or non-substantial. The Chief Investigator will ensure that any required study amendments are submitted to the appropriate body for approval, including substantial amendments that require review by NHS REC. Amendments will be communicated to relevant stakeholders and will not be implemented until all required approvals have been received. Amendments will be recorded in the study data file and will be reflected with revision of the study protocol, tracked using version numbers.

All correspondence with the REC will be retained and reporting completed as requested including notification to the REC of the end of the study. Annual progress reporting will be the responsibility of the Chief Investigator.

## **7.3 Patient and Public Involvement**

People with lived experience of inflammatory arthritis have been central to developing our proposal. They will remain integral to our project, and work alongside our research team providing insights, challenges and advice.

Two public contributors with inflammatory arthritis have developed this project alongside us ([name] and [name]). With appropriate training, they will lead our public involvement activities supported by two public engagement facilitators in Palliative Care and Rheumatology services. [name] will also co-lead Study 3 with [name]. Input from [name] and [name] into this application reflects our aim to ensure meaningful public engagement is included in our research. Acting as co-applicants and members of the Project team they bring a wealth of lived experience of inflammatory arthritis.

We plan to engage with more public contributors at key stages in the project. Those people who contributed to our project preparation focus group and 1:1 meetings, have agreed to remain involved with the project and to be consulted as it progresses. We also have agreed access to Bristol Rheumatology Patient Group and Bath Institute for Rheumatic Diseases membership. We will seek the views of people from

these groups at key time points in the application, in addition to the contributions from [name] and [name]:

- The co-creation of explanatory videos on PSC and inflammatory arthritis with Leon! Animations
- Content and design of recruitment materials
- Interview topic guide
- Review of Study 1 draft qualitative themes to inform dissemination of findings and Study 2 survey items
- Summary of key findings for stakeholder focus groups
- Dissemination strategy

Public contributors will be paid for their time and expertise according to NIHR payment guidance.

